Appendix 24. SJC66 / TJC68: Swollen and Tender Joint Count

An overview of the (66 / 68) joints to be assessed bilaterally are provided below:

- Temporomandibular
- Sternoclavicular
- Acromioclavicular
- Shoulder
- Elbow
- Wrist
- Metacarpophalangeal: first, second, third, fourth, fifth
- Proximal interphalangeal: first, second, third, fourth, fifth
- Distal interphalangeal: second, third, fourth, fifth
- Hip¹
- Knee
- Ankle
- Tarsus
- Metatarsophalangeal: first, second, third, fourth, fifth
- Proximal interphalangeal (toe) : first, second, third, fourth, fifth

Replaced / missing (or otherwise not assessable) joints should be documented at Day 1 and omitted from further evaluation during the study.

¹ Assessed for tenderness only

Appendix 25. LDI: Leeds Dactylitis Index

Dactylitis has been defined as "uniform swelling such that the soft tissues between the metacarpophalangeal and proximal interphalangeal, proximal and distal interphalangeal, and/or distal interphalangeal joint and digital tuft are diffusely swollen to the extent that the actual joint swelling could no longer be independently recognised."⁽¹⁾ Dactylitis is a hallmark clinical feature in patients with spondyloarthropathies (SpA) and is commonly observed in psoriatic arthritis.

Dactylitis occurs in 16-48% of cases of psoriatic arthritis (PsA). Acute dactylitis has been shown to be a clinical indicator of disease severity in PsA; conversely, chronic, non-tender diffuse dactylitic swelling may be less clinically significant⁽²⁾. Dactylitis is due to inflammation in the majority of tissues in the digit - the tendon sheaths, joints, bones and soft-tissues in between⁽³⁾. Recurrent dactylitis, often in the same digit(s), may be the only clinical manifestation of PsA.

The only validated tool for assessing dactylitis is the Leeds Dactylometer⁽⁴⁾. The validity of this instrument has been assessed using the OMERACT filter. The instrument and tool have demonstrated good evidence of responsiveness in a clinical trial⁽⁵⁾. In addition, the instrument incorporates a definition of dactylitis (a 10% difference in the ratio of circumference of the affected digit to the contralateral digit). Using the contralateral digit as a normalizer enables any inter-individual variation in measurement technique to be minimised. The instrument comes with an assessment sheet (see reverse) which provides automatic computation of the Leeds Dactylitis Index.

How to use the Leeds Dactylometer

1. The fingers and toes are visually inspected by the examiner. Those digits which look dactylitic are measured.
2. Slip the loop of the Dactylometer around the base of the digit adjacent to the web space. Pull the indicator strip tight so that the base of the digit blanches slightly (see illustration). The collar of the device should be firmly pressed against the base of the digit, as illustrated.
3. Record the circumference in mm on the Dactylometer record sheet
4. Repeat the procedure on the contralateral digit
5. If both ipsilateral and contralateral digits are thought to be dactylitic then use the reference range (given at the foot of the sheet) as the comparator.

6. Only record the digits with a 10% difference in circumference

Appendix 26. PhGADA: Physician's Global Assessment of Disease Activity

Physician's global assessment of disease activity

Place a mark on the line below to indicate PsA disease activity (independent of the subject's self-assessment):

BMI	body mass index
CCI	
BSA	body surface area
CASPAR	Classification Criteria for Psoriatic Arthritis
CBC	complete blood count
CI	confidence interval
eCRF	electronic case report form
COVID-19	coronavirus (2019 nCoV)
CRP	C-reactive protein
csDMARDs	conventional synthetic disease-modifying anti-rheumatic drugs
CSR	clinical study report
CTCAE	Common Terminology Criteria for Adverse Events
DAPSA	Disease Activity in Psoriatic Arthritis
DAS28	disease activity score for 28 joint count
DMC	data monitoring committee
ECG	electrocardiogram
EDC	electronic data capture
eCRF	electronic case report form
EQ-5D-5L	EuroQoL 5 Dimensions with 5 Levels
ET	early termination
FACIT-Fatigue	Functional Assessment of Chronic Illness Therapy-Fatigue
FAS	full analysis set
GI	gastrointestinal
GSI	Gilead Sciences
HAQ-DI	Health Assessment Questionnaire-Disability Index
HLGT	high-level group term
HLT	high-level term

HRQoL	health-related quality of life
HCRU	healthcare resource utilization questionnaire
hsCRP	high-sensitivity C-Reactive Protein
ID	identification
IPD	important protocol deviation
IXRS	interactive voice/web response system
LDA	low disease activity
LDI	Leeds Dactylitis Index
LLOQ	lower limit of quantitation
LLT	lower-level term
LOQ	limit of quantitation
LS	least squares
LTE	long-term extension
MACEs	major adverse cardiovascular events
MCS	mental component score
MDA	Minimal Disease Activity
MedDRA	Medical Dictionary for Regulatory Activities
MI	multiple imputation
MMRM	mixed model repeated measures
MNAR	missing not at random
MRI	Magnetic Resonance Imaging
MST	MedDRA search term
MTX	methotrexate
NRI	non-responder imputation
NRS	numerical rating scale
NSAIDs	non-steroidal anti-inflammatory drugs
OC	observed case
PASDAS	Psoriatic Arthritis Disease Activity Score
PASI including BSA	Psoriasis Area and Severity Index including Body Surface Area
PASI75	Psoriasis Area and Severity Index 75% improvement
PCS	physical component summary
PD	pharmacodynamics
PGADA	Patient's Global Assessment of Disease Activity
PGAPI	Patient's Global Assessment of PsA Pain Intensity
PhGADA	Physician's Global Assessment of Disease Activity
PhGAP	Physician's Global Assessment of Psoriasis
PK	pharmacokinetic
PP	per-protocol
PROs	patient reported outcomes
PsA	psoriatic arthritis

PsAID-12	12-item Psoriatic Arthritis Impact of Disease
PsAMRIS	Psoriatic Arthritis Magnetic Resonance Imaging Score
PsARC	Psoriatic Arthritis Response Criteria
PT	preferred term
PTM	placebo to match
Q1, Q3	first quartile, third quartile
q2w	once every two weeks
q.d.	quaque die (each day)
SAE	serious adverse event
SAP	statistical analysis plan
SBP	systolic blood pressure
SD	standard deviation
SE	standard error
SF-36v2	36-item short form survey version 2
SJC/TJC	Swollen and Tender Joint Count
SMQ	standardized MedDRA query
SOC	system organ class
SPARCC Enthesitis Index and LEI	Spondyloarthritis Research Consortium of Canada Enthesitis Index and Leeds Enthesitis Index
TDC	tender dactylitis count
TEAE	treatment-emergent adverse event
TFLs	tables, figures, and listings
ULN	upper limit of normal
VAS	visual analog scale
VLDA	Very Low Disease Activity
WBC	white blood cell
WHO	World Health Organization
WPAI-PsA	Work Productivity and Activity Impairment for Psoriatic Arthritis

1. INTRODUCTION

This statistical analysis plan (SAP) describes the statistical analysis methods and data presentations to be used in tables, figures, and listings (TFLs) in the clinical study report (CSR) for Study GS-US-431-4566. This SAP is based on the study protocol amendment 2 dated 17 April 2020 and the electronic case report form (eCRF). The SAP will be finalized before database finalization. Any changes made after the finalization of the SAP will be documented in the CSR.

1.1. Study Objectives

The primary objective of this study is as follows:

- To evaluate the effect of filgotinib compared to placebo in active PsA as assessed by the American College of Rheumatology 20% improvement (ACR20) response at Week 12

The secondary objectives of this study are as follows:

- To evaluate the effect of filgotinib on core domains of psoriatic arthritis (PsA, e.g. peripheral arthritis, psoriatic skin disease, enthesitis and dactylitis) as assessed by Minimal Disease Activity (MDA), Very Low Disease Activity (VLDA), ACR responses, Psoriasis Area and Severity Index including Body Surface Area (PASI including BSA) responses, Spondyloarthritis Research Consortium of Canada Enthesitis Index and Leeds Enthesitis Index (SPARCC Enthesitis Index and LEI), Leeds Dactylitis Index (LDI), Psoriatic Arthritis Disease Activity Score (PASDAS), Disease Activity Index for Psoriatic Arthritis (DAPSA), Modified Nail Psoriasis Area and Severity Index (mNAPSI), and Physician's Global Assessment of Psoriasis (PhGAP)
- To evaluate the effect of filgotinib on physical function in active PsA as assessed by Health Assessment Questionnaire-Disability Index (HAQ-DI)
- To evaluate the effect of filgotinib on fatigue and quality of life in active PsA as assessed by Functional Assessment of Chronic Illness Therapy - Fatigue Scale (FACIT-Fatigue), 36-item Short-Form Health Survey Version 2 (SF-36v2), and 12-item Psoriatic Arthritis Impact of Disease (PsAID-12)
- To evaluate the efficacy of filgotinib versus adalimumab in active PsA as assessed by ACR20 response
- To evaluate the safety and tolerability of filgotinib

CCI

1.2. Study Design

This is a randomized, double-blind, active-controlled, Phase 3 study in adult male and female subjects with active PsA who have had an inadequate response or intolerance to 1 or more therapies for PsA, such as conventional synthetic disease-modifying anti-rheumatic drugs (csDMARDs), apremilast and / or non-steroidal anti-inflammatory drugs (NSAIDs), but have never received a biologic DMARD (bioDMARD) for PsA or psoriasis.

The study consists of two parts, the Main Study: Screening through Week 16 (inclusive), and the Long Term Extension (LTE): after Week 16 up to approximately 2.25 years.

Part 1 – Main Study (Screening through Week 16):

Approximately 854 subjects will be randomized in a 2:2:1:2 ratio to one of 4 dosing groups as outlined below.

Randomization will be stratified by geographic region, concurrent use of conventional synthetic DMARD(s) (csDMARDs) and / or apremilast at randomization (yes or no)

Dosing groups in the Main Study:

- Filgotinib 200 mg group: **filgotinib 200 mg once daily** + placebo to match (PTM) filgotinib 100 mg once daily + PTM adalimumab subcutaneous (SC) injection once every two weeks (q2w)
- Filgotinib 100 mg group: PTM filgotinib 200 mg once daily + **filgotinib 100 mg once daily** + PTM adalimumab SC injection q2w

- Active comparator group: PTM filgotinib 200 mg once daily + PTM filgotinib 100 mg once daily + **adalimumab 40 mg SC injection q2w**
- Placebo control group: PTM filgotinib 200 mg once daily + PTM filgotinib 100 mg once daily + PTM adalimumab SC injection q2w

NOTE: All subjects will discontinue adalimumab / PTM injections by the Week 16 Visit (the last injections should be at approximately Week 14).

Part 2 – LTE (After the Week 16 Visit for 2 years):

After completion of the Main Study, subjects who have not permanently discontinued study drug will continue on to the LTE as follows:

[figure not shown]
- Those who were assigned to the filgotinib groups will continue on the same study drug assignments
- Those who were assigned to the placebo or active comparator group will be reassigned 1:1 in a blinded fashion to filgotinib 200 mg or 100 mg once daily

Dosing groups in the LTE:

- Filgotinib 200 mg group: **filgotinib 200 mg once daily** + PTM filgotinib 100 mg once daily
- Filgotinib 100 mg group: PTM filgotinib 200 mg once daily + **filgotinib 100 mg once daily**

For the first 16 weeks of study participation, subjects who temporarily interrupt or permanently discontinue study drug for any reason are to continue with study visits and assessments through the Week 16 Visit, per protocol Section 3.5 unless the subject withdraws consent, is lost to follow-up, and / or continued participation in the study is medically contraindicated, per investigator's judgment. Study drug interruption and discontinuation considerations are outlined in protocol Section 3.5. All subjects who permanently discontinue study drug should continue to receive standard of care treatment for their PsA including additional therapies, if required.

Figure 1-1. Study Design

1.3. Sample Size and Power

Sample size is determined based on the non-inferiority test of each filgotinib group compared to the adalimumab group on the ACR20 response rate at Week 12. When assuming the ACR20 response rate being 52% and 60% for the adalimumab and each filgotinib group, and 38.6% for the placebo group, 244 subjects in each filgotinib group and placebo group, and 122 subjects in the adalimumab group are required to obtain 90% power at a two-sided 0.025 significance level to demonstrate that filgotinib group preserves more than 50% of the effect of adalimumab with respect to the ACR20 response rate at Week 12.

A sample size of 244 subjects in each filgotinib group and the placebo group will provide over 95% power to detect a difference in ACR20 response rate of 21.4% at Week 12 (38.6% and 60% for the placebo group and each filgotinib group, respectively) using a two-sided 0.025 significance level superiority test.

In summary, the total sample size will be approximately 854 subjects per original planning.

The study was terminated per Sponsor’s decision after 67 subjects had been enrolled. At study termination, 13 out of 67 subjects continued on to the LTE, and 7 of those 13 subjects were terminated immediately after entering LTE phase. All the other subjects were prematurely discontinued from or completed the Main Study visits.

2. TYPE OF PLANNED ANALYSIS

2.1. Final Analysis

After study early termination, the final analysis will be performed for all enrolled subjects. Final analysis will occur after outstanding data queries have been resolved or adjudicated as unresolvable, and the data have been cleaned and finalized.

3. GENERAL CONSIDERATIONS FOR DATA ANALYSES

Analysis results will be presented using descriptive statistics. For categorical variables, the number and percentage of subjects in each category will be presented; for continuous variables, the number of subjects (n), mean, standard deviation (SD) or standard error (SE), median, first quartile (Q1), third quartile (Q3), minimum, and maximum will be presented.

By-subject listings will be presented for all subjects in the All Randomized Analysis Set and sorted by subject identification (ID) number, visit date, and time (if applicable). Data collected on log forms, such as AEs, will be presented in chronological order within the subject. The treatment group to which subjects were randomized will be used in the listings. Age, sex at birth, race, and ethnicity will be included in the listings, as space permits.

Given the small number of subjects who entered LTE phase, for all the efficacy and safety analyses, unless specified otherwise, all the analyses and summary tables will be generated based on the data during Main Study phase (for subjects enrolled under Protocol Amendment (PA) 1 who stayed in Main Study beyond Week 16 visit, only the data up to Week 16 visit will be included). All the data will be presented in the listing.

3.1. Analysis Sets

Analysis sets define the subjects to be included in an analysis. Analysis sets and their definitions are provided in this section. The analysis set will be identified and included as a subtitle of each table, figure, and listing.

For each analysis set, the number and percentage of subjects eligible for inclusion, will be summarized by treatment group.

A listing of reasons for exclusion from analysis sets will be provided by subject.

3.1.1. All Randomized Analysis Set

All Randomized Analysis Set includes all subjects who were randomized in the study. This is the primary analysis set for by-subject listings.

3.1.2. Full Analysis Set

The Full Analysis Set (FAS) includes all randomized subjects who took at least 1 dose of study drug. The study drugs in this study are filgotinib 200 mg, filgotinib 100 mg, adalimumab and PTMs. This is the primary analysis set for efficacy analyses.

3.1.3. Safety Analysis Set

The Safety Analysis Set includes all subjects who took at least 1 dose of study drug. This is the primary analysis set for safety analyses.

3.2. Subject Grouping

For analyses based on the All Randomized Analysis Set and FAS, subjects will be grouped according to the treatment to which they were randomized. For analyses based on the Safety Analysis Set, subjects will be grouped according to the actual treatment received. The actual treatment received will differ from the randomized treatment only when their actual treatment differs from randomized treatment for the entire treatment duration of each treatment phase.

The treatment groups during the Main Study phase are:

- Filgotinib 200 mg once daily
- Filgotinib 100 mg once daily
- Adalimumab q2w
- Placebo

The treatment groups during the LTE phase are:

- Filgotinib 200 mg once daily
- Filgotinib 100 mg once daily
- Adalimumab switch to filgotinib 200 mg once daily
- Adalimumab switch to filgotinib 100 mg once daily
- Placebo switch to filgotinib 200 mg once daily
- Placebo switch to filgotinib 100 mg once daily

3.3. Strata and Covariates

Subjects will be randomly assigned to treatment groups via the interactive voice or web response system (IXRS) in a 2:2:1:2 ratio to filgotinib 200 mg, filgotinib 100 mg, adalimumab or placebo control using a stratified randomization schedule. Stratification will be based on the following variables:

- Geographic region (Group A includes the following countries: Australia, Canada, New Zealand, Spain, and United States; Group B includes the following countries: Bulgaria, Poland, Group E includes Japan)
- Concurrent use of conventional synthetic DMARD(s) (csDMARDs) and / or apremilast at randomization (Yes or No)

List of csDMARD and/or apremilast is provided in [Appendix 6](#).

If there are discrepancies in stratification factor values between the IXRS and the clinical database, the values recorded in the clinical database will be used for analyses.

For efficacy endpoints, stratification factors and the baseline value of the efficacy variable(s) will be included as a covariate in the efficacy analysis model, as specified in Section 6. Given the small number of subjects in geographic region Group E, Group B and E will be combined as a single group in all the efficacy modeling.

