4.2. Inclusion Criteria

Subjects must meet all of the following inclusion criteria to be eligible for participation in this study.

- 1) Male or female subjects who are 18-75 years of age (19-75 years of age at sites in Republic of Korea, 20-75 years of age at sites in Japan and Taiwan) on the day of signing initial informed consent
- 2) Meet CASPAR and have a history consistent with PsA ≥ 6 months at Screening
- 3) Have active PsA defined as ≥ 3 swollen joints (from a 66 SJC) and ≥ 3 tender joints (from a 68 TJC) at Screening and Day 1; these may or may not be the same joints at Screening and Day 1
- 4) Must have a documented history or active signs of at least one of the following at Screening:
 - a) Plaque psoriasis
 - b) Nail changes attributed to psoriasis
- 5) Have had inadequate response or intolerance to ≥ 1 csDMARD, apremilast and / or NSAID, administered over the course of ≥ 12 weeks for the treatment of PsA, as per local guidelines / standard of care
- 6) If continuing csDMARD(s) during the study, subjects are permitted to use only a maximum of 2 of the following drugs and must have been on this treatment for ≥ 12 consecutive weeks prior to Screening, with a stable dose and route of administration (defined as no change in prescription) for ≥ 4 weeks prior to Day 1:
 - a) MTX oral or SC up to 25 mg / week (must include concomitant use of a folic / folinic acid supplementation as per local standard of care / investigator judgment; MTX use may not be combined with leflunomide during the study)
 - b) Leflunomide up to 20 mg once daily orally (may not be combined with MTX during the study)
 - c) Sulfasalazine up to 3 g daily orally

- d) Hydroxychloroquine up to 400 mg daily or chloroquine up to 250 mg daily
 - e) Apremilast up to 30 mg twice daily orally
 - f) Azathioprine up to 200 mg daily orally
 - g) Cyclosporine up to 300 mg daily orally
- 7) If csDMARDs are stopped prior to Day 1, the following washout periods are required:
- a) ≥ 4 weeks prior to Day 1: apremilast, sulfasalazine, azathioprine, MTX, hydroxychloroquine
 - b) ≥ 8 weeks prior to Day 1: oral cyclosporine
 - c) Leflunomide must either have a washout period of ≥ 8 weeks prior to Day 1 or ≥ 4 weeks prior to Day 1 if 11 days of standard cholestyramine therapy was completed
- 8) If taking NSAIDs, dose must be kept stable (defined as no change in prescription) for ≥ 2 weeks prior to Day 1

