4. SUBJECT DISPOSITION

4.1. Subject Enrollment and Disposition

A summary of subject enrollment will be provided by treatment group and overall for each country within each geographic region and investigator within a country. The summary will present the number and percentage of subjects enrolled. For each column, the denominator for the percentage calculation will be the total number of subjects analyzed for that column.

A similar enrollment table will be provided by randomization stratum. The denominator for the percentage of subjects in the stratum will be the total number of enrolled subjects. If there are discrepancies in the value used for stratification assignment between the IXRS and the clinical database, the value collected in the clinical database will be used for the summary. A listing of subjects with discrepancies in the value used for stratification assignment between the IXRS and the clinical database at the time of data finalization will be provided.

The randomization schedule used for the study will be provided as an appendix to the CSR.

A summary of subject disposition will be provided by treatment group and study phase (Main Study and LTE). This summary will present the number of subjects screened, the number of subjects who met all eligibility criteria but were not randomized with reasons subjects not randomized, the number of subjects randomized, and the number of subjects in each of the categories listed below:

- Safety Analysis Set
- Full Analysis Set
- Completed study drug (Main Study phase)
- Did not complete study drug with reasons for premature discontinuation of study drug (Main Study phase)
- Entered LTE phase
- Did not complete study drug with reasons for premature discontinuation of study drug (LTE phase)
- Did not complete the study with reasons for premature discontinuation of study in Main Study and LTE phase respectively

For the status of study drug and study completion and reasons for premature discontinuation, the number and percentage of subjects in each category will be provided. The denominator for the percentage calculation will be the total number of subjects in the Safety Analysis Set corresponding to that column.

The following by-subject listings will be provided by subject ID number in ascending order to support the above summary tables:

- Reasons for premature study drug or study discontinuation
- Reasons for screen failure (will be provided by screening ID number in ascending order)

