5.2. Baseline Disease Characteristics

Baseline disease characteristics include:

- Concurrent use of csDMARD and/or apremilast at randomization (Yes or No) and daily or weekly dose taken at randomization by medication
 - Only csDMARD and/or apremilast medication records with a start date prior to randomization date and an end date on or after randomization date or missing will be used for counting the number of subjects with csDMARD and/or apremilast use at randomization.
 - Only csDMARD and/or apremilast medication records with a start date prior to randomization date and an end date on or after randomization date or missing that have a valid dose, dose unit, and dosing frequency will be used for summarizing daily or weekly dose taken at randomization.

- Oral Corticosteroids use on Study Day 1 (Yes or No) and daily dose taken on Study Day 1
 - Only oral Corticosteroid medication records with a start date prior to Study Day 1 and an end date on or after Study Day 1 or missing will be used for counting the number of subjects with oral Corticosteroid use on Study Day 1.
 - Only oral Corticosteroid medication records with a start date prior to Study Day 1 and an end date on or after Study Day 1 or missing that have a valid dose, dose unit, and dosing frequency will be used for summarizing daily dose taken on Study Day 1.
 - All oral Corticosteroid medications' doses will be converted to prednisone equivalent dose (conversion chart is in [Appendix 3](#)).
 - If multiple oral Corticosteroid medications are taken on Study Day 1, the total daily dose will be the sum of those medications' doses at Study Day 1 after conversion.
- Topical Corticosteroids use on Study Day 1 (Yes or No)
 - Only topical Corticosteroid medication records with a start date prior to Study Day 1 and an end date on or after Study Day 1 or missing will be used for counting the number of subjects with topical Corticosteroid use on Study Day 1.
- NSAIDs use on Study Day 1 (Yes or No)
 - Only NSAIDs medication records with a start date prior to Study Day 1 and an end date on or after Study Day 1 or missing will be used for counting the number of subjects with NSAIDs use on Study Day 1.
- Duration of PsA from diagnosis (years)
 - Calculated as $((\text{first dose date}) - (\text{date of initial diagnosis}) + 1 \text{ day}) / 365.25$. If the date of initial diagnosis is incomplete, then the following rules will be applied:
 - missing day: use the first of the month

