6.2.2. Primary Analysis of the Primary Efficacy Endpoint

To test for superiority of filgotinib 200 mg or filgotinib 100 mg group versus placebo control group in proportion of subjects who achieve ACR20 at Week 12, a logistic regression analysis with treatment groups and stratification factors in the model will be used. The model will include all treatment groups. Missing data on the ACR20 response rate at Week 12 will be imputed using multiple imputation (MI) assuming missing at random (MAR):

- The MI procedure replaces each missing binary ACR20 value with a set of plausible values that represent the uncertainty about the right value to impute. Twenty imputed datasets will be generated with starting seed 12345. These multiple imputed data sets are then analyzed by using the same method for the primary analysis for complete data as specified above. The results from each set of imputed data sets will then be combined using Rubin’s rule {[Rubin 1987](#)}. The stratification factors and treatment groups will be included in the imputation model as covariates and all available data at post-baseline visits up to Week 16 visit will be included in the longitudinal model.

The p-value from the logistic regression model with MI for testing the superiority of filgotinib 200 mg or filgotinib 100 mg as compared to placebo will be provided. The 2-sided 95% confidence interval (CI) of the ACR20 response rate at Week 12 based on MI method will be provided for each treatment group. In addition, treatment difference in ACR20 response rate at Week 12 between each filgotinib dose group and placebo group along with its 95% CI calculated based on MI method will be provided.

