Appendix 6. Lists of PsA Medications

1) List of bioDMARDs and Investigational bDMARDs (WHO Preferred Terms)

- ABATACEPT
- ADALIMUMAB
- ALEFACEPT
- BIMEKIZUMAB
- BRODALUMAB
- CERTOLIZUMAB PEGOL
- ETANERCEPT
- GOLIMUMAB
- GUSELKUMAB
- INFLIXIMAB
- IXEKIZUMAB
- SECUKINUMAB
- TOCILIZUMAB
- USTEKINUMAB

2) List of csDMARDs (WHO Preferred Terms)

- AZATHIOPRINE
- CICLOSPORIN
- HYDROXYCHLOROQUINE SULFATE
- IGURATIMOD
- LEFLUNOMIDE
- METHOTREXATE
- METHOTREXATE SODIUM
- SULFASALAZINE

3) List of Corticosteroids (WHO Preferred Terms)

- BETAMETHASONE ACETATE;BETAMETHASONE SODIUM PHOSPHATE
- BETAMETHASONE BUTYRATE PROPIONATE;MAXACALCITOL
- BETAMETHASONE DIPROPIONATE;BETAMETHASONE SODIUM PHOSPHATE
- BETAMETHASONE DIPROPIONATE;CALCIPOTRIOL
- CLOBETASOL
- CLOBETASOL PROPINOATE
- CORTISONE
- DEFLAZACORT
- METHYLPREDNISOLONE
- METHYLPREDNISOLONE ACETATE
- METHYLPREDNISOLONE SODIUM SUCCINATE
- PREDNISOLONE
- PREDNISOLONE VALEROACETATE
- PREDNISON
- TRIAMCINOLONE
- TRIAMCINOLONE ACETONIDE

4) List of NSAIDs (WHO Preferred Terms)

- ACECLOFENAC
- CELECOXIB
- CODEINE PHOSPHATE;IBUPROFEN
- DEXKETOPROFEN TROMETAMOL
- DICLOFENAC
- DICLOFENAC POTASSIUM

- DICLOFENAC SODIUM
- ESOMEPRAZOLE MAGNESIUM;NAPROXEN
- ETODOLAC
- ETORICOXIB
- IBUPROFEN
- KETOPROFEN
- LOXOPROFEN SODIUM DIHYDRATE
- MELOXICAM
- NABUMETONE
- NAPROXEN
- NAPROXEN SODIUM
- NIMESULIDE
- SULINDAC
- TENOXICAM

GS-US-431-4566-SAP-v1.0

ELECTRONIC SIGNATURES

Signed by	Meaning of Signature	Server Date (dd- <small>MMM</small> - <small>yyyy</small> hh:mm:ss)
PPD	Clinical Research eSigned	16-Jul-2021 23:30:19
PPD	Biostatistics eSigned	20-Jul-2021 00:37:49

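### Does the absence of apremilast and chloroquine from the SAP's medication lists put the csDMARD/apremilast stratification factor at risk?

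*SAP*

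**What the plan says.** SAP 3.3 defines two stratification factors: geographic region, and concurrent csDMARD and/or apremilast use at randomization (yes or no). For the drugs behind the second factor it states "List of csDMARD and/or apremilast is provided in" Appendix 6. That appendix holds four lists: bioDMARDs, csDMARDs, corticosteroids and NSAIDs. The relevant one is headed "List of csDMARDs (WHO Preferred Terms").

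Protocol 4.2, criterion 6, sets out the background drugs a subject may continue. Two of its entries are "Apremilast up to 30 mg twice daily orally" and "Hydroxychloroquine up to 400 mg daily or chloroquine up to 250 mg daily".

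Where IXRS and the database disagree on a stratum, SAP 3.3 says that "the values recorded in the clinical database will be used for analyses". SAP 4.1 applies the same rule to the enrollment table: "the value collected in the clinical database will be used for the summary". The same section plans a listing of subjects whose values disagree.

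SAP 5.2 counts background use for the baseline table from dated entries: "Only csDMARD and/or apremilast medication records with a start date prior to randomization date" and an end date on or after that date, or missing, are counted.

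The factor enters the logistic model for ACR20 at Week 12, and SAP 6.2.2 adds that "The stratification factors and treatment groups will be included in the imputation model as covariates". It also enters the key secondary logistic models and the MMRM in SAP 6.3.2.

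**The concern.** A reader who follows the pointer in SAP 3.3 finds a list that cannot fully define the factor. Apremilast is half of the factor's name and appears in none of the lists. Chloroquine is a permitted background drug in the protocol and is named nowhere in the SAP.

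The rule that the database overrides IXRS makes this look serious. Suppose the database stratum is programmed from coded medication records using only the Appendix 6 terms. A subject whose sole background drug is apremilast or chloroquine would then be coded No, and that No would replace a correct Yes from IXRS. The wrong value would enter the primary logistic model, its imputation model, the key secondary logistic models and the MMRM. The SAP never says that this is how the value is built, and it never says that it is not. A list of WHO preferred terms, placed in the section on strata, does suggest derivation from coded records.

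**Working it through.** **1. Compare the lists.** Protocol 4.2, criterion 6, items a to g, names 8 drugs. The csDMARD list in SAP Appendix 6 has 8 terms; methotrexate takes two of them, so it covers 7 distinct drugs.

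| Protocol 4.2, criterion 6 | SAP Appendix 6 |
|---|---|
| Methotrexate | Yes (two terms) |
| Leflunomide | Yes |
| Sulfasalazine | Yes |
| Hydroxychloroquine | Yes |
| Chloroquine | No |
| Apremilast | No |
| Azathioprine | Yes |
| Cyclosporine | Yes |
| (not listed) | Iguratimod |

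Covered: 8 − 2 = 6 of 8. The omissions are real, and no redaction mark is visible in the appendix.

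**2. Ask what each omission can do.**

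*Apremilast.* The factor names it, so no list is needed to identify it. SAP 5.2, the only written record-selection rule for a characteristic of this name, names it too. Coding an apremilast-only subject as No would contradict both sections. What is left is an incomplete cross-reference.

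*Chloroquine.* It is covered only by the general term csDMARD. Two conditions must both hold before a model is affected: (a) the stratum is derived from the Appendix 6 terms, and (b) at least one of the 67 subjects took chloroquine and no other qualifying drug. The documents establish neither. On (a), SAP 3.3 speaks of values recorded and SAP 4.1 of a value collected, which fits an eCRF field at least as well as a derivation. On (b), no count of chloroquine users is given.

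**3. See which outputs use the factor.** It is used in the logistic, imputation and MMRM models. The observed-case response rates and unstratified differences in SAP 6.3.2 and 6.4.2 do not use it. SAP 3.4 and 6.1 make every p-value nominal, and SAP 6.5 drops the graphical testing procedure, so no formal rejection depends on it.

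**4. Size, if some subjects were recoded.** Each subject is 1/67 = 1.5% of the sample. A simulation gives a scale for the effect.

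- From the documents: 67 subjects; the 2:2:1:2 ratio, giving 19:19:10:19 for 200 mg, 100 mg, adalimumab and placebo (67 × 2/7 = 19.1; 67/7 = 9.6); ACR20 rates of 60%, 60%, 52% and 38.6% (SAP 1.3).
- Assumed: stratum Yes in 50% or 70% of subjects; stratum–response odds ratio of 1 or 2; two region groups split 50:50; no missing data.
- Model: logistic regression on treatment, stratum and two-level region, 1,500 runs per scenario.
- Measure: |log OR after recoding − log OR before| / SE, for 200 mg versus placebo.

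| Subjects recoded Yes to No | Median shift (SE), range over scenarios | 95th percentile (SE), range over scenarios |
|---|---|---|
| 1 | 0.025–0.041 | 0.10–0.15 |
| 3 | 0.039–0.060 | 0.18–0.25 |
| 5 | 0.047–0.076 | 0.22–0.32 |

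If no subject is affected, the shift is exactly zero. With no missing data, the simulation covers the logistic route only; it does not test the imputation model or the MMRM.

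**The case for a change.** The best case for acting is that the pointer is wrong on its face and correcting it costs almost nothing: two drug entries and one sentence on the data source. A collected yes/no field would not need a list of coded terms, so placing one in the strata section suggests derivation from records. The planned listing would expose a recoded subject, but the override rule would still settle the disagreement in favour of the database. Even if the model stratum is an eCRF field, the baseline table in SAP 5.2 is built from medication records, and the only csDMARD list the SAP supplies has no chloroquine.

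Part of this stands. The cross-reference is incomplete, the source of the stratum is unwritten, and a chloroquine-only subject could be missed in the baseline summary. What does not stand is the step from there to a distorted analysis. For apremilast, that step needs a programmer to disregard the factor's own name. For chloroquine, it needs a derivation the SAP does not describe and a subject the documents do not show. Appendix 6 is also not offered as a copy of criterion 6, since it includes iguratimod. The SAP was written after enrollment stopped at 67, so the list may reflect coded terms actually seen. That is inference, and the SAP does not say so.

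**Conclusion.** No change to the plan is needed. This is a clerical gap in an appendix together with a data source left unstated, and an analyst can fill both sensibly: count apremilast because the factor names it, count chloroquine because the protocol places it among the permitted csDMARDs, and look at any subject who appears on the IXRS-versus-database listing.

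The effect on the models is zero if the stratum is a collected field or if nobody took chloroquine as the only qualifying drug. If 1 to 5 of 67 subjects were recoded, the median shift in the 200 mg versus placebo log odds ratio would be about 0.03 to 0.08 standard errors, with 95th percentiles of 0.10 to 0.32. Those figures rest on the assumed stratum prevalence, stratum effect and region split, on complete data, and on recoding counts chosen for illustration. The conclusion would be different only if the stratum were in fact programmed from Appendix 6 alone and the discrepancy listing showed subjects moved from Yes to No for that reason. Even then, the affected results would be nominal model-based ones in a trial stopped at 67 of about 854 planned subjects.
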